We will leverage two ongoing dissemination initiatives to support our recruitment goals: Project BEST (Bringing Evidence-Supported Treatment to South Carolina), a statewide dissemination initiative funded since 2007 by The Duke Endowment; and the Program on Adolescent Traumatic Stress (PATS), a regional initiative funded by SAMHSA since 2011. Together, as of June 2016, 30 learning collaboratives have been completed via Projects BEST and PATS with 799 clinicians (over 600 of whom are study eligible), 166 senior leaders, and > 3,500 child training cases. Drs. [name] and [name] (Co-Is) co-lead these projects and fostered the agency partnerships that will support the proposed effectiveness-implementation trial (see letters of support), including 4 sites that served as partners in our R34. Projects BEST and PATS are not explicitly linked to the study except that they will establish the population of eligible providers from which we will recruit. Each dissemination initiative maintains a roster of providers who completed TF-CBT training within the past 10 (BEST) or 5 (PATS) years. We will use this combined roster of over 600 study-eligible providers to identify candidates for recruitment (see Milestones).

Notably, Projects BEST and PATS offer training agency-wide, not through a selective or competitive process. More than two-thirds of providers in these agencies (~70%) complete the training, resulting in an externally valid sample of providers that is diverse with respect to years of experience, race/ethnicity, and other key variables. The learning collaborative process is comparable to that of other regional or national dissemination initiatives community-based providers may encounter.⁷⁹⁻⁸¹ **Recency of training is also highly variable. Only 109 of 602 rostered study-eligible providers (18.1%) completed their training within the past year.** This ensures that our sample will be diverse with respect to training recency. Finally, even among recently trained providers, we have found that knowledge and skill is highly variable. For example, we found mean post-training TF-CBT Knowledge scores of 61% in a survey of 39 providers who recently completed training via PATS.⁸²

C2. NIMH R34 Phase 1: Semi-Structured Interviews with TF-CBT Certified National Trainers.

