Phase 1 of our R34 was to complete individual semi-structured interviews with 21 nationally certified mental health treatment trainers, who guided development of the initial tablet-toolkit concept.⁴⁵ Data from this pilot were used to determine the components of treatment that are vulnerable to drift and activities that might assist in overcoming challenges to child engagement and provider fidelity in each component of the model.^{45,47,83}

C3. NIMH R34 Phase 2: Development of Tablet-Facilitated TF-CBT

The development process for tablet TF-CBT is described in detail in our recently published protocol paper.⁶¹ Tablet TF-CBT consists of 11 “Chapters.” Introductory videos, which are available on the launch screen of each chapter, depicts a child who explains the rationale for the activity and briefly (i.e., 1 min) demonstrates the key elements of the chapter. Additional videos are brief clips designed to help providers reinforce concepts or skills taught in treatment. Some chapters feature interactive touch-screen games, such as drag-and-drop activities, drawing tools, trivia-style card games, and animated relaxation activities. **Each activity was developed to address an element of the TF-CBT protocol that was identified by experts and providers as challenging to implement with high fidelity and engagement.**

[figure not shown]
C4. NIMH R34 Phase 3: Qualitative Testing of Tablet TF-CBT. Qualitative testing was completed via focus groups with mental health providers (n=22) and focus groups and individual interviews with youth aged 8-16 years (n=24). Both samples had strong racial diversity; child focus groups were stratified by age (8-11 vs. 12-16 years).

Interviews were transcribed, independent coders produced a content analysis, and thematic categories emerged. These data guided revision of the tablet toolkit in preparation for the feasibility pilot.⁴⁷

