C5. NIMH R34 Phase 4: Randomized Controlled Feasibility Trial. We recently completed our R34 in which we conducted a randomized controlled feasibility trial to demonstrate our proposed methodology. This approach is consistent with expert recommendations to pilot test the feasibility of methods to be used in large RCTs, use data yielded by such studies to de-bug the methodology, and assess optimal strategies to execute the RCT.⁸⁴ We proposed an 8-month feasibility trial with recruitment of 10 providers from 4 local community-based clinics in SC. We aimed to recruit 20 families (referred by participating providers) during months 1-4 of the 8-month trial. Consistent with our current proposal, our research team managed all of the research elements of the trial. We conducted all consents, study assessments, random assignments, and coding and analysis of audiorecorded sessions uploaded by the providers. Providers referred patients to the study only after completing a standard intake process and determining that TF-CBT was the treatment of choice for that patient. Partnering sites were not engaged in research elements of the trial and delivered standard care (TF-CBT) to all study patients. Half of the providers were given access to the tablet TF-CBT toolkit, but there were not any requirements for providers with access to use the toolkit or any elements within the toolkit. They were given a 45-min training session to ensure that they knew how to navigate the toolkit, but were told that they were welcome to use it (or not) in whatever way they wished based on their own perceptions around how it may be helpful (or not) in their delivery of standard treatment. We proposed these benchmarks for establishing feasibility:

- **Recruitment of 20 families into the feasibility trial over our proposed 4-month recruitment period**
- **Completion of the treatment protocol by 14 families (70%)**
- **Retention of at least 14 families (70%) through post-treatment assessments**
- **Providers audiorecord at least 90% of all treatment sessions in both conditions**
- **Children, caregivers, and providers express high satisfaction with tablet-based TF-CBT**

Figure 1. Sample Screenshots

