All mental health treatment sessions will be videorecorded and coded for fidelity and engagement by coders blind to study purpose and hypotheses. Videorecording of sessions is standard and typical in clinical practice for trainers or supervisors to review session recordings; in fact, most of the providers on the roster of eligible providers for this study recorded sessions while receiving training and ongoing consultation in TF-CBT.

Providers will be randomly assigned to treatment condition (tablet-facilitated vs. standard TF-CBT). Providers assigned to the tablet condition will be provided a unique study id to minimize risk of contamination. The tablet TF-CBT platform will not be accessible without a study-assigned userid. Eligible providers will have been fully trained in TF-CBT via ongoing dissemination initiatives independent of this study and will carry active child trauma cases. Each provider will treat three families during the course of the trial. We chose to recruit 400 providers and 3 families per provider, instead of fewer providers with more families per provider (e.g., 70 and 5), to minimize threats associated with provider turnover and variable patient caseloads. Providers will not be informed of their condition until their initial study-eligible family has been enrolled under their care. Although we discussed the possibility of integrating a tablet-based resource into the control condition to facilitate patient blinding, our agency partners were not receptive to this.

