
feel that it is important to retain in our study families who decline video-recording but accept audio-recording. In our tablet TF-CBT pilot study, sessions were audio-recorded; only 1 of our 27 participating families declined the audio-recording of sessions. Moreover, toward the end of our pilot study, we submitted an addendum to our IRB application permitting us to ask questions addressing families' perceptions about video-recording sessions; all families asked these questions reported that they felt that video-recording sessions was acceptable. Therefore, we anticipate that most families will agree to video-recording of sessions. Providers will be informed that the project is not a condition of employment and will not affect their employment in any way, that they will not be penalized if they decline to participate, that measures are confidential, that they may withdraw at any time, and that study data are not part of their employment records. Additionally, providers will be explained the process of randomization as well as assignment to study condition.

Inclusion Criteria

Mental health providers from across the state and from partnering community-based clinics nationwide, will be recruited for this study. Most providers from all of these clinics meet the full inclusion criteria listed below.

1. full- or part-time employment at one of the participating clinics
2. must have obtained at least a Master's degree in social work, counseling, clinical psychology, or a related field
3. consistent caseload of potentially eligible children and families (i.e., appropriate candidates for TF-CBT)
4. trained in the implementation of TF-CBT

Exclusion Criteria

We attempted to limit exclusion criteria so that we have as ecologically valid a sample as possible. There are no primary exclusion criteria for the providers.

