Child/Family Recruitment. We propose to recruit a total of 360 children and their caregivers. Participants will include children, ages 8-16 years, who are referred from clinics with participating providers for symptoms related to potentially traumatic event exposure (e.g., physical or sexual abuse, witnessed violence, disaster or serious accident), and a guardian with physical custody of the child (e.g., biological or adoptive parent, foster parent, grandparent, aunt/uncle). Participants of all races, genders, and ethnic backgrounds will be eligible. We anticipate adequate representation of racial/ethnic minority children in this sample based on demographic data available via training cases under Project BEST and PATS. However, we will carefully track recruitment of racial/ethnic minorities and will oversample African American and Hispanic children if our recruitment trajectories fall meaningfully beneath our projections.

Inclusion/exclusion criteria (below) are consistent with previous studies that have documented the efficacy of the TF-CBT protocol. Child age range was chosen based on recommendations of national trainers ([name] et al., 2014), feasibility of administering standardized child assessments by telephone, suitability of the treatment protocol and tablet toolkit model, and prior research samples. Families will be recruited from clinics with mental health providers who have consented to participate in the study. Partnering clinics will introduce the study to potentially eligible families. Families that are interested in participating in the study will complete a small contact form that acknowledges their interest in being contacted by our study team to learn more about the project. This will be shared with our team. We will then contact the family, determine eligibility, consent families that are interested in participating, and schedule/complete the baseline interview. The administration of consent/assent and all study assessments will be conducted by an independent, trained study evaluator who is blind to condition. Interested families will be consented and assented (children ages 8 to 16) by the project clinical interviewer via teleconsent (either through Doxy.me or RedCAP). The Charleston-Dorchester and Berkeley Department of Mental Health clinics were participants in our R34 pilot study. After several

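### Providers given the toolkit in the R34 feasibility trial may enrol again and be randomised to standard TF-CBT; the likely effect is a small attenuation, and a one-line exclusion or a flag would deal with it

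*Protocol*

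**What the plan says.** Protocol Section E.1.a lists four provider inclusion criteria. Two of them are "full- or part-time employment at one of the participating clinics" and "trained in the implementation of TF-CBT"; the others are a Master's degree and a suitable caseload. On exclusions it says "There are no primary exclusion criteria for the providers", and explains that the team wanted a sample close to routine practice. Section D4c gives a shorter inclusion list and no exclusions.

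The pilot sites return. Section C1 describes the agency partnerships behind this trial as "including 4 sites that served as partners in our R34". Section E.1.a adds that "The Charleston-Dorchester and Berkeley Department of Mental Health clinics were participants in our R34 pilot study" and makes consent arrangements for families referred from those clinics to the present study.

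On the pilot itself, Section C5 reports that "Half of the providers were given access to the tablet TF-CBT toolkit", with a 45-minute training session. It also reports that 17 providers consented and 13 treated study families.

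On contamination, Section D4b gives tablet-arm providers an individual study ID and states: "The tablet TF-CBT platform will not be accessible without a study-assigned userid". Providers do not learn their arm until their first family is enrolled (D4b, D4d). Neither document uses earlier toolkit exposure as an exclusion, a stratification factor or a named covariate, and it is not among the provider characteristics listed for collection in D4l.

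**The concern.** The trial compares providers with and without the toolkit on fidelity and engagement. These are the outcomes of Hypotheses 1 and 2 and the mediators in Hypotheses 4 and 5. The login stops a control provider from opening the app. It does not remove activities already learned, or ways of structuring a TF-CBT component picked up while using the toolkit with pilot families. Section D3 expects only limited further development, so what those providers used is close to what is now being tested.

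Two things are at stake. Former users in the standard arm may retain part of the benefit, which brings the arms together. Former users in the tablet arm arrive with practice, so their results do not reflect only the roughly 50-minute training described in D4e. In both cases the estimate moves away from the effect of giving the toolkit to providers who have not used it. As written, the plan would neither prevent nor detect this.

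**Working it through.** The plan gives no figure on this point to reproduce. The check has two parts: whether the route is open, and how large the effect could be.

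**Is the route open?** A pilot toolkit user who still works at one of the four returning sites would meet the employment criterion. Pilot providers delivered TF-CBT, so they should meet the training criterion. Nothing in D4c or E.1.a then keeps them out, and D4d allocates them to either arm. One link is not explicit: recruitment draws on the BEST and PATS training rosters (C1, D4c, E.1.a), and the documents do not say that each pilot provider is on one.

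**Inputs**
- Pilot providers: 17 consented, 13 active (C5). Half had the toolkit, so E = 13/2 = 6.5 to 17/2 = 8.5, or 6 to 9 people.
- Total providers J: at least 120 (SAP 2.9.1; Protocol D1 also gives 60 per arm), 250 (E.1.a) or 400 (D4b and elsewhere). The documents do not agree, so all three are shown.
- Assumptions: all former users re-enrol (an upper bound) and allocation is 1:1.

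**Exposed controls.** Expected number = E/2 = 3.25 to 4.25. Share of the standard arm = (E/2)/(J/2) = E/J. With 6 re-enrolled users, the chance that at least one is a control is 1 − 0.5^6 = 98.4%; with 9 it is 1 − 0.5^9 = 99.8%.

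**Attenuation.** If an exposed control keeps a fraction r of the toolkit effect, and the effect in the tablet arm is the same for everyone, the contrast shrinks by the fraction r × E/J. The documents give no value for r. The table shows r = 0.5 and the extreme r = 1.

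| J | Share of controls, E/J | Shrinkage, r = 0.5 | Shrinkage, r = 1 |
|---|---|---|---|
| 120 | 6.5/120 = 5.4% to 8.5/120 = 7.1% | 2.7% to 3.5% | 5.4% to 7.1% |
| 250 | 2.6% to 3.4% | 1.3% to 1.7% | 2.6% to 3.4% |
| 400 | 1.6% to 2.1% | 0.8% to 1.1% | 1.6% to 2.1% |

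**Tablet arm.** If earlier practice adds a fraction q of the effect for former users in that arm, the net shrinkage is (r − q) × E/J. It is toward the null unless q exceeds r, and the same small share E/J limits its size.

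**The case against.** The open criteria are a deliberate choice with a stated reason: a sample that resembles routine practice. Exposure precedes randomisation, so the arms are balanced on it in expectation and the comparison by assigned arm stays valid for the providers enrolled. Coders record iPad activity on the session form (D4h), so actual tablet use in a control session would be visible, and D8a and D8b allow provider-level covariates. Re-enrolment is not reported and could be zero. The protocol is dated March 2022 and its planned timeline ends in early 2021, so a new exclusion may come too late.

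Most of this stands, and it limits the size of the point without removing it. The routine-practice argument is the weakest part, because people who used the experimental toolkit before the trial are not typical future adopters. The coding form records tablet use, not what a provider learned earlier, and no named covariate captures R34 history.

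A reader might go further and count the R34 focus-group providers (21 in Section A, 22 in Section C4). With 22 added and no overlap, the upper share at 120 providers becomes (8.5 + 22)/120 = 25.4%. The documents do not support that figure. Section A calls these providers only local, and neither section gives their clinics, current employment or roster status. They are a possible further source but should not be counted as eligible. Nor do the documents support reading this as confounding: randomisation rules that out, and what remains is mild attenuation and a blurred contrast.

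**Conclusion.** The gap is real but narrow. As written, R34 toolkit users can be enrolled and allocated to standard TF-CBT, and the plan would not record that it had happened. If all 6 to 9 returned, 3 to 4 controls would be affected, and at half retention the loss in the Hypothesis 1 and 2 contrasts would be under 4% at any of the three stated trial sizes. That rests on full re-enrolment, 1:1 allocation, an assumed retention of one half and no extra practice benefit in the tablet arm. The documents permit re-enrolment; they do not say it will occur. This is a cheap improvement, not a threat to the trial's validity.

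**What to change.** In Protocol D4c and in the provider exclusion criteria of E.1.a, exclude providers who were given access to the tablet toolkit in the R34 feasibility trial.

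If any have already been randomised, keep them in the intention-to-treat analysis. Flag R34 toolkit access, and focus-group participation where known, from the R34 records. Add to SAP 2.9.1 a pre-specified sensitivity analysis that reports the Hypothesis 1 and 2 contrasts with and without their cases (at most 9 × 3 = 27 cases, at three per provider).

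The cost is the loss of at most about 9 of the 602 rostered providers in C1 (9/602 = 1.5%), some of them probably engaged and easy to recruit. The team ran the R34 consents and assignments (C5), so it should be able to identify these providers, although the documents do not say that a usable list is held. No new data collection from providers or families is needed.

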2. ADEQUACY OF PROTECTION AGAINST RISKS

a. Recruitment and Informed Consent

- *Describe plans for the recruitment of subjects (where appropriate) and the process for obtaining informed consent. If the proposed studies will include children, describe the process for meeting requirements for parental permission and child assent.*
- *Include a description of the circumstances under which consent will be sought and obtained, who will seek it, the nature of the information to be provided to prospective subjects, and the method of documenting consent.*

A family can be referred under the condition that the child has experienced a potentially traumatic event and is a possible candidate for TF-CBT delivered by one of the study clinicians. In these cases, the referring party will obtain verbal consent for the family to be contacted by project staff for the purpose of conducting an initial phone screen. The initial phone contact will be conducted by the clinical study interviewer and structured to determine potential eligibility and schedule an appointment to obtain informed consent and conduct the initial assessment. Study staff will contact the family within 48 hours of referral into the project. For cases involving alleged child abuse, the intake coordinator at each clinic will determine if an alleged incident has been reported to authorities and investigated prior to referring

to the study. If the case has not been investigated, it will be referred to an investigative agency (DSS, law enforcement). This is unlikely to occur, because it is a standard procedure followed by all (or virtually all) of our partnering clinics, who have consistently maintained active caseloads of children affected by traumatic events and therefore have clear policies in place to guide assessment and treatment of such cases. Nevertheless, if it does occur and such a referral must be made, we may facilitate assignment of such cases to providers outside of the scope of the study to minimize risk that study involvement will delay receipt of treatment, which could occur if the investigation (i.e., substantiation or determination of a credible report) is open for longer than one month. Caregivers recruited into the study will be informed that any new (i.e., unreported) disclosures of abuse must be reported to the appropriate authorities, as mandated by state law.

To reduce the burden of participating in research, we will use of the RedCAP or Doxy.me tele-consenting technology. Teleconsent through RedCAP will allow the study interviewer to conduct the consent/assent process over the telephone. The interviewer will send the teleconsent link to the family and call them on the telephone. The family will be able to read consent/assent/HIPAA forms along with the provider and will have the ability to sign, date, and download their own copy all via the secure, and HIPAA compliant RedCAP system. Doxy.me was developed and is maintained by MUSC Biomedical Informatics Center (BMIC). The BMIC tele-consent application is built upon an established telemedicine platform (Doxy.me), and allows researchers to discuss a study with potential participants via video chat, where they may also share with participants the IRB-approved Consent and HIPAA forms. This enables both parties to collaboratively complete and sign documents in real-time in a location that is convenient for them. For example, Doxy.me allows a researcher to remotely guide the participant through a consent document step-by-step and help them fill out the necessary fields. This includes synchronous viewing, scrolling, zooming, and editing of the consent document. As the researcher moves their mouse, clicks, scrolls, zooms the page, or edits fields (e.g., text, checkboxes, radio buttons) on the consent document, the actions simultaneously appear on the participant's screen (and vice versa). Once the informed consent document has been completed, a PDF of the document can be generated and available to both the researcher and participant, which can be printed or saved on the local computer and printed. This process has been piloted successfully with a number of clinical populations. Through tele-consent, an independent and trained project staff member will remotely guide the legal guardian through a consent document step-by-step and help them fill out the necessary fields. Once the informed consent document has been completed, a PDF of the document can be generated and is available to both the researcher and the participant.

A separate written consent will be completed by participating providers, who will be visited in person by a member of our research team ([name], [name], [name], or [name], or other designated study staff). Provider consent will be obtained in-person following completion of the study orientation at partnering clinics. For providers who are unable to complete the in-person orientation, they will have the option to complete the orientation via webinar at which time will be send a link to teleconsent via RedCAP. Agency supervisors and senior leaders will not be consented as study participants. If participating in Aim 4 interviews, supervisors and senior leaders will complete a waiver of signed consent.

Any participant (i.e., child, caregiver, provider, supervisor, or senior leader) may withdraw his or her consent at any time and may withdraw from the study at any time without prejudice or loss of benefits to which they are otherwise entitled. All adult participants will be asked for written consent after reading the consent form, discussing the study, and being given a chance to ask questions. They will be informed that they are being asked to participate in a research study. They will be told the nature of the procedures and randomization, informed of risks associated with their participation, asked to read the consent form, and encouraged to ask questions or discuss any pertinent issues. They will be told that declining to serve as a participant in this study will not influence or compromise the quality of their care or state of employment at the various institutions.

b. Protection against Risk

- *Describe planned procedures for protecting against or minimizing potential risks, including risks to confidentiality, and assess their likely effectiveness.*
- *Where appropriate, discuss plans for ensuring necessary medical or professional intervention in the event of adverse effects to the subjects.*
- *Studies that involve clinical trials (biomedical and behavioral intervention studies) must include a description of the plan for data and safety monitoring of the research and adverse event reporting to ensure the safety of subjects in Section 4 below.*

Each child will receive psychological treatment by an experienced clinician trained in TF-CBT, who is being supervised by their agency supervisor. In addition, several investigators on the study team (e.g., Drs. [name], [name], [name], [name]) are licensed mental health care providers with extensive experience and training certification in TF-CBT. The expertise of the team assures that we are well equipped to manage any adverse events that occur in the context of treatment. The following procedures will be instituted to minimize the risk to participants.

Confidentiality. Emphasis on confidentiality will be stressed in all aspects of the study. No information about participation in the study will be divulged without specific and written consent to release information. The only exception would be mandated reporting of new allegations of child abuse or disclosures of intent to harm self or others. These confidentiality limits will be documented in the written consent form and verbally explained to all participants. Research records of individual participants will only be identified by code rather than by name. For all phases of the project, providers also will be informed that the project is not a condition of employment, that they will not be penalized if they decline to participate, that measures are confidential, that they may withdraw at any time, and that study data are not part of their employment records. Child (ages 8 to 16), parent, and provider assent, consent, and HIPAA documents and signed information releases (as requested by patients) are the only documents containing patient identifiers and will be kept separate from study records in a locked cabinet on a secure floor.

Data Safety. With regard to data safety issues, [name] of Fuzzco, Inc., will work with [name], of MUSC's TACHL Center to support electronic data security. [name] and the Fuzzco team, and [name] and the TACHL team, have extensive experience safeguarding the security and integrity of sensitive materials, including protected health information and sensitive financial information. The secure servers that will house the data files collected from the tablet TF-CBT resource, provider metrics, and study interview assessments are located at MUSC in SSL (Secure Sockets Layer) 128-bit encrypted servers behind firewalls. During each stage of the study, Fuzzco and TACHL will facilitate access to study data sets as needed. Respondent confidentiality will be masked in all data files by the use of project identification numbers rather than personal information. All other electronic records, including video-recordings of sessions, are de-identified in collection and will be maintained in password protected locations on the secure server. All paper records will be de-identified and maintained in a locked file cabinet on a secure floor. The only document linking participants with identification numbers will be retained in an encrypted file on the secure server with access limited to the key study personnel. Data presented at professional meetings or published in journals or books will not allow identification of individual participants. These procedures are expected to minimize any potential adverse effects from participating in this study.

Assessment Procedures. As described in the research plan, families will complete assessments conducted by study staff at baseline, and at 3-, 6-, 9-, and 12-months post-baseline. The assessments will be conducted via telephone for several reasons. First, in-person interviews are cost prohibitive because we are recruiting families from a large geographic area across three states. Second, it would also be cost prohibitive to arrange televideo post-baseline assessments with all families. We believe that scheduling a small number of baseline interviews for new patients in collaboration with partnering clinics will be a challenging but manageable process, and we already have taken several steps toward identifying these processes with these clinics. However, it is impractical and cost prohibitive to coordinate 1,800 assessments (5 assessments x 360 participants) with our partnering clinics throughout the course of the study. Third, efforts to coordinate televideo assessments through the

clinics for all 1,800 assessments would have clear adverse effects on study retention because this would increase burden associated with transportation and time for families. Fourth, research has shown that telephone assessments are acceptable and methodologically appropriate for children as young as 8 years old, which corresponds to our lower age range for children recruited into the study. Taken together, the use of telephone methodology for post-baseline assessments will ensure that study costs, data quality, retention of participants, and burden to families associated with scheduling and transportation are all manageable and reasonable within the scope of the proposed study.

Although unlikely, should an individual become uncomfortable during the assessment, the interviewer will provide assistance or direct families to other sources of support. Many victims of crime and other traumatic events rarely report that being asked about their traumatic events is distressing. Zajac et al (2011) reported findings from a nationally representative sample of 3,614 adolescents who completed telephone-based surveys asking about exposure to physical and sexual assault, community and domestic violence, or other serious accidents. Only 5.7% of the youth interviewed found any of the interview upsetting, of which only 0.2% remained upset at the time the phone interview concluded. Only 2 (<0.1%) participants were upset enough to want to speak with a counselor at the conclusion of the interview.

Study Consent and Participant Incentives. Consent and HIPAA forms containing identifying information will be maintained securely and separately from other research materials. Measures will be taken to maximize confidentiality and include the following: (1) names of participants will appear only on consent and HIPAA forms and a digitally secure, password protected master roster; (2) only key study personnel will have access to the complete list of names and respondent ID numbers; (3) all other data will be referred to by ID numbers only. Treatment sessions will be video-recorded for fidelity and engagement coding purposes. Audiorecording will be offered as an alternative to families who decline video-recording. These recordings will be kept secure and separate from identifying information, and coding ratings of the sessions will not include identifying information. Following coding and analyses, the recordings will be destroyed. The likelihood that these methods will effectively protect the confidentiality of participants is considered to be extremely high.

The consent for the RCT Trial for caregivers, children, and providers will include agreement to video-record treatment sessions and to complete assessment measures throughout the project. At consent, child participants and their caregivers will also be informed about and given a rationale for randomization. They will not be notified of their condition (to which the clinical interviewer will be blind), and will not be able to predict their condition until they begin treatment. An initial evaluation will be conducted with all potentially eligible families by study staff. This will include a structured diagnostic interview as well as completion of self-report measures. Participants with symptoms of psychosis or personality disorder, suicidal or homicidal risk, severe cognitive impairment, or developmental disability that, in the judgment of the investigator, will make it unlikely that the patient can adhere to the study regimen will be excluded from the study. These participants may be offered other, more appropriate treatment options in the clinic or referrals that may be available based on the judgment of treating providers within the partnering clinic. All interviews and associated transcriptions will not contain any identifying information and will be maintained in a secure and password protected research drive only accessible to study personnel.

The consent will also explain that participating families will be mailed a gift card upon completion of the study assessments. The reimbursement schedule is as follows: baseline (\$30), 3-month (\$30), 6-month (\$40), 9-month (\$40) and 12-month (\$50) post-baseline assessments. A small number of families ($n = 20$) also will be purposively sampled to complete qualitative post-treatment interviews for which they will receive additional compensation (\$50). Provider, supervisor, and senior leader consent forms will explain that we will not be able to offer monetary incentives for participation in this study due to agency rules and regulations regarding the use of incentives during working hours. However, they will be informed the study iPads will be donated to the clinic following completion of study procedures: one iPad for each participating provider who completes the study. Additionally, provider consent forms will

state that providers who complete the qualitative interview on the use of the toolkit outside of work hours will receive additional compensation (\$50).

